The product being used is a commercially available product, known as "Crest Whitening Emulsions", will be used as the investigative product. There will be no active control group. This is not the first time P&G whitening gel will be used in humans. We do believe this is the first study investigating dry mouth sensation from using a whitening gel.

- III) Research Plan
 - A) Experimental Design

This will be a single center, two visit study investigating the effectiveness of dryness in the oral cavity, whiteness of teeth, and teeth sensitivity after one week's use of whitening agent.

B) Sample Size and Statistical Analysis

Sample size

This is a single site study. All study-related procedures will take place at TUSDM. Based on our preliminary data from a previous study, we anticipate 25 subjects will be needed to achieve the necessary statistical power required to observe expected differences in relief of dryness in the oral cavity. Because we anticipate the potential of many screen failures due to the VAS scale and saliva production requirements outlined in the exclusion/inclusion criteria section, we will screen/enroll a total of 100 subjects to conservatively account for potential dropouts or screening failures.

Statistical analysis

The subjects will be asked to complete one questionnaire each visit. Completing the first part before the application of the study product, and completing the second part after the application of the study product, as directed on the questionnaire. The self-reported scores from the visual analogue scales (VAS) will be considered on the first and final visit. The salivary flow before and after the application of the product, Pre & Post-Product Use Dry Mouth & Sensitivity Questionnaire before and after the product application will be compared using a student -t test method. The same method will be used to make comparisons of these gathered data points between the first and final visits.

Randomization

This will be an open label study; thus no randomization plan is necessary.

Blinding

There will be no blinding for this study.

C) Products

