The investigational product to be used in this study is manufactured by P&G and called, "Crest Whitening Emulsions". The amount of each dose should be enough to cover the entire tip of the whitening wand, approximately ½ a tsp. The use of the study product in this study will be for what they are approved for. Per the manufacturer's instructions, study subjects will be asked to apply the study product up to 4 times a day.

Procter and Gamble will be supplying the study product gel to the study team. IDS will not be involved in this study.

The investigative product to be used in this study is a hydrophobic emulsion containing agent (a teeth whitening gel with emulsification gel). It contains:

Petrolatum, Water, Hydrogen Peroxide, Flavor, Sucralose, Sorbitan Palmitate

D) Subject Characteristics

- 1) Inclusion Criteria
 - At least 18 years of age.
 - The inability to produce more than < 0.18mL/min of unstimulated saliva.
 - Score of 5 or more on question 1 of the VAS dry mouth scale (How severe is your dryness right now?), evaluated in the Pre-Product Use Dry Mouth & Sensitivity Questionnaire .
 - Evidence of currently taking Xerostomia-inducing medication such as, antihypertensives, anti-anxiety agents, psychiatric remedies, antihistamines.
 - Subject not currently using any teeth whitening or desensitizing products
 that contain potassium nitrate such as Sensodyne or Pronamel.
 - Subject willing to comply with the study regimen and products.

2) Exclusion Criteria

- Subjects who are currently pregnant (self-reported).
- Subjects able to produce more than 0.18mL/min of unstimulated saliva

- Subjects that have ever received therapeutic radiation in the head and neck area.
- Subjects with a diagnosis of conditions that would affect salivary flow such as Sjogren's Syndrome.
- Subjects with a condition the investigator believes not suitable for the study such as autoimmune diseases that impact salivary flow.
- Subjects that currently use whitening toothpaste, desensitizing toothpaste, or any other products causing similar results.
- Subjects currently participating in any other research studies.
- Subject unable to provide consent (ex. Cognitively impaired adults).
- Non-English speaking

3) Subject Withdrawal/Termination Criteria

- Subjects who do not comply with the study procedures, such as use of teeth whitening products, may be withdrawn from the study.

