- The subjects will be asked to read the informed consent form (ICF). Subjects will
 be given ample time to have any questions answered. If a subject decides to
 participate, he or she will be asked to sign the ICF. A copy of the ICF will be given
 to the subject.
- 3. Subject will be asked to complete demographic information and a medical history.
- 4. An oral exam, including evaluation of oral cavity, soft and hard tissues, will be completed following standard of care procedures in US dentistry using a mouth mirror and dental explorer.
- 5. Subject medications with potential side effects being dry mouth will be verified using the Physician's Reference Desk.
- 6. Saliva Collection 1 (pre-product application): Saliva will be collected by asking subjects to do nothing but drool into a pre-weighed vial for 5 minutes (referred to as the Drooling Method). The post collection weight will be subtracted from the pre-weight to determine the flow rate. The saliva samples will be discarded after they are weighed.
- A paper questionnaire will be given to subject to complete before application of study product and after application of study product. Questionnaire includes Visual Analogue Scale (VAS) questionnaire on dry mouth, quantity of saliva, and perceived sensitivity of teeth.

- 8. Inclusion/exclusion criteria will be evaluated and eligibility for the study will be determined.
- 9. Demonstration and application of study product:
 - a. A visual and oral demonstration of application of the whitening gel will be performed by a study team member. The script for the demonstration will be the one provided in the information packet in each study product box so the subject can bring the instructions home. The study team member will mimic the necessary steps to properly apply the gel, without using the product. The study team member will then have the subject complete the steps while applying the gel to their own teeth. Subjects will then be asked to sit for 5 minutes to let the gel set on their teeth.
- 10. Saliva Collection 2 (post-product application): Saliva will be collected using the same Drooling Method as Saliva Collection 1. The saliva samples will be discarded after they are weighed.

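### The Visit 1 dryness score that admits subjects is also the baseline for the one-week t test, so with no control arm and no second baseline part of any fall is expected from regression to the mean

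*Combined protocol and SAP*

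**What the plan says.** The primary aim (section I.A) is a reduction in self-reported oral dryness. Section III.D.1 admits subjects on "Score of 5 or more on question 1 of the VAS dry mouth scale (How severe is your dryness right now", read from the pre-product questionnaire. Section III.D.2 excludes "Subjects able to produce more than 0.18mL/min of unstimulated saliva".

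Visit 1 is both screening and baseline (section III.F). Unstimulated saliva is collected at step 6. At step 7, "A paper questionnaire will be given to subject to complete before application of study product and after application of study product". At step 8, "Inclusion/exclusion criteria will be evaluated and eligibility for the study will be determined". The gel is first applied at step 9. Section III.B provides one questionnaire per visit, so there is a single pre-treatment dryness score and it is the qualifying one.

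Under Statistical analysis in section III.B, saliva flow and questionnaire scores "before and after the product application will be compared using a student -t test method", and then "The same method will be used to make comparisons of these gathered data points between the first and final visits". The text does not say whether the t test is paired or which comparison addresses the primary aim. Section II states "There will be no active control group" and section III.B states "This will be an open label study; thus no randomization plan is necessary". Regression to the mean is not mentioned.

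**The concern.** Question 1 asks about dryness at that moment. A subject who clears the cutoff partly because of a bad moment will tend to score lower next time, treated or not. When the qualifying reading is reused as the baseline, that drift is counted as improvement. A control arm would show the same drift and let it be subtracted. A baseline on a separate day, not used for selection, would remove it. The plan has neither.

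The plan itself expects selection to matter: section III.B anticipates many screen failures from the dryness and saliva requirements and screens 100 people for 25. Followed exactly, it could report a significant one-week fall as relief when some or all of it came from how subjects were chosen, and the reader would have no figure to judge it against. The saliva limit works the same way in the other direction: subjects chosen for low flow will tend to show higher flow later.

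**Working it through.** **The plan's own figure.** The 25 subjects cannot be reproduced, because section III.B gives no alpha, power, effect size or SD. Working backwards, a paired t test with n = 25 and two-sided 0.05 has 80% power for a standardized change of 0.58. That is a yardstick for the biases below.

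**Inputs.** From the documents: cutoff 5, n = 25, no control, one pre-treatment score. Assumed: 0-10 scale, two-sided 0.05, screened mean 4-7, SD 2-2.5, visit-to-visit correlation ρ of 0.5-0.9, no product effect.

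**Formula.** With a = (5 − mean)/SD and λ = φ(a)/[1 − Φ(a)], the expected one-week fall among those selected is (1 − ρ) × SD × λ. The variance of the change is (1 − ρ)² × SD² × (1 + aλ − λ²) + SD² × (1 − ρ²).

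**Worked case: mean 5, SD 2.5, ρ 0.7.**
- a = 0, so λ = 0.399/0.5 = 0.798.
- Expected fall = 0.3 × 2.5 × 0.798 = 0.60 points.
- Variance of change = 0.09 × 6.25 × (1 − 0.637) + 6.25 × 0.51 = 0.20 + 3.19 = 3.39, so SD = 1.84.
- Standardized fall = 0.60/1.84, about 0.32, against the yardstick of 0.58.

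**Range.** Simulated with scores clipped to 0-10, selection at 5 or more, n = 25 and no product effect. The nominal rate of significant falls is 2.5%.

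| Screened mean, SD | ρ | Fall (points) | Significant fall, paired | Unpaired |
|---|---|---|---|---|
| 4, 2.5 | 0.5 | 1.33 | 82% | 75% |
| 4, 2 | 0.5 | 1.14 | 87% | 81% |
| 5, 2.5 | 0.5 | 0.99 | 58% | 45% |
| 5, 2.5 | 0.7 | 0.60 | 36% | 14% |
| 5, 2.5 | 0.9 | 0.20 | 14% | under 1% |
| 6, 2 | 0.7 | 0.30 | 17% | 3% |
| 7, 2 | 0.5 | 0.29 | 11% | 4% |
| 7, 2 | 0.9 | 0.06 | 5% | 0% |

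**The other planned dryness comparisons** (if question 1 is repeated after application; mean 5, SD 2.5, visit ρ 0.7, within-visit correlation 0.9):
- Visit 1 pre/post: (1 − 0.9) × 2.5 × 0.798 = 0.20 points, 14% significant (paired).
- Visit 1 post against Visit 2 post: the entry score is not used, but Visit 1 post is a same-day reading on selected subjects and carries part of the elevation. (0.9 − 0.7) × 2.5 × 0.798 = 0.40 points, 18% significant (paired).
- Visit 2 pre/post: 0.00 points, about 2.5% significant.

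**Can screening data bound the effect?** Without clipping, the fall equals (1 − ρ) × (mean of selected minus mean of all screened). At mean 5, SD 2.5 with clipping, the gap is 1.95 and the formula gives 0.98, 0.59 and 0.20 at ρ 0.5, 0.7 and 0.9, against simulated 0.99, 0.60 and 0.20. Selection on saliva as well makes it approximate. If half the candidates pass the saliva limit and saliva correlates 0.5 with underlying dryness:

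| ρ | True fall | Reference: all screened | Reference: met saliva limit |
|---|---|---|---|
| 0.5 | 0.80 | 1.07 | 0.73 |
| 0.7 | 0.47 | 0.65 | 0.41 |
| 0.9 | 0.15 | 0.22 | 0.13 |

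In this scenario the two references bracket the true fall. The saliva-flow bias itself was not quantified.

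**The case against.** The study is titled exploratory, is openly single-arm and unblinded, and states no alpha or success criterion, so a limitation statement might seem enough. The magnitude rests entirely on assumed values: 87% is a corner of the grid, and an unpaired test often gives rates near or below nominal. The post-product items are not shown, so it is not certain that question 1 feeds any pre/post test, and no section names question 1 as the primary endpoint.

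Most of this stands as a limit on the claim. It does not remove the point. The one-week comparison of question 1 needs only the pre-product part, which is given at both visits. A missing control is disclosed; selection on the baseline is a separate and predictable bias that is not. The exploratory label does not change what the t tests compare.

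Four stronger readings are tempting and not supported:
- **That an observed fall would be mostly artefact.** Without the screened distribution and correlation, the documents cannot show this.
- **That every comparison is compromised.** Visit 2 pre/post is essentially free of this selection, though still uncontrolled.
- **That a fall larger than a calculated allowance demonstrates a product effect.** The allowance needs an assumed ρ. If the display stopped at ρ 0.5 and the true value were 0.4 or 0.3, the lower confidence limit would exceed it in about 5% or 10% of trials with no effect. Placebo response would remain in any case.
- **That low Visit 2 scorers will be dropped.** The Visit 2 eligibility review (step 3) precedes the questionnaire (step 7), and the schedule lists evaluation of eligibility criteria at Visit 1 only. The termination wording in section III.D.3 has no time limit, however, and withdrawn subjects' data are excluded, so confirmation is needed.

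**Conclusion.** The point holds in this form and should be fixed. The direction of the bias follows from the documents alone: the qualifying score is the only pre-treatment score, it is the baseline for the one-week t test, and nothing in the design can separate regression to the mean from relief. Visit 1 post against Visit 2 post is also affected if question 1 is repeated, although it does not use the entry score.

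The size is not determinable from the documents. On the stated assumptions it runs from negligible (0.06 points, 5% significant falls) to dominant (about 1.3 points; up to 87% in the least favourable cell), with 0.60 points and 36% in a middle case. It is minor if most candidates score well above 5 or visit-to-visit correlation is near 0.9. Confidence in the direction is high; confidence in any particular magnitude is low.

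**What to change.** In the Statistical analysis paragraph of section III.B:

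1. Analyse the one-week change in question 1 (Visit 1 pre minus Visit 2 pre) with a paired t test and 95% confidence interval. State that this change includes regression to the mean and placebo response and is not by itself evidence of a product effect.
2. Label every comparison that uses a Visit 1 value, pre or post, for dryness and for saliva, as affected by selection at Visit 1. Report Visit 2 pre/post separately (paired, if question 1 is repeated) as the immediate-relief comparison not subject to this selection, noting that it is still uncontrolled and open label.
3. Add a descriptive sensitivity display, with no pass/fail reading, of the expected fall: (1 − ρ) × (mean question 1 of analysed subjects minus mean of the reference group). Use a range of ρ extending below 0.5, for example 0.3 to 0.9, and two reference groups: everyone screened at Visit 1, and those who met the saliva limit. State that ρ is assumed and that selection on saliva makes the figure approximate. Do not apply this formula to saliva flow. Keep question 1 for every screened subject in the screening log described in section III.N, and clarify that the exclusion of withdrawn subjects' data in section III.D.3 does not bar this summary use of screen-failure scores.
4. Reconcile section III.D.3 with the Visit 2 step order in section III.F by confirming that no subject is left out of the analysis because of the Visit 2 question 1 score or saliva flow.

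The cost is analysis wording and one log column, since question 1 is already completed before eligibility is decided. The price is a more cautious one-week conclusion. A second baseline is not a cheap substitute: taken on the same day it would leave 0.40 of the 0.60-point bias (visit ρ 0.7, within-visit 0.9), and on a separate day it adds a visit.

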Exploratory Study on Effect of Whitening Agent with Emulsion Gel in Xerostomic Population

Principal Investigator: [name], DMD, MS

Co-Investigators: [name], DMD, PhD

Study Coordinators:

[name], AS, CDA, CCRP

[name], BS, CCRP

[name], RDH [name]

Study Location: Tufts University School of Dental Medicine

[name]

Sponsor: Procter & Gamble

Protocol Version Date: 4/14/2023

Exploratory Study on Effect of Whitening Agent with Emulsion Gel in Xerostomic Population [name], DMD, MS

I) Introduction

A) Aim/Hypothesis/Objective

Objectives:

- Primary aim: To see a reduction in the self-reported subjective perception of dryness in the oral cavity.
- Secondary aims: To measure self-reported sensitivity of the teeth, self-reported
 perception of teeth whiteness, and objective measurement of improvement of saliva
 production.

II) Background and Rationale

Xerostomia, is a subjective sensation of dryness of the mouth, which may have a significant effect in a persons quality of life. The sensation of dryness of the mouth may be caused by autoimmune diseases which attack the saliva producing glands irreversibly e.g., salivary glands, or the sensation of dryness could be caused by therapeutic radiation, which can destroy the salivary glands at the genetic level and impede their functions. Additionally, there are more than 700 medications including antihypertensives, anti-anxiety agents, psychiatric remedies, and antihistamines that can effect neural transmission. Neural transmission is when the neuro transmission is hindered reversibly leading to the salivary hypofunction that results in dry mouth. It is estimated that 12-47% of the elderly and 10-19.3% in their early 30's suffer from dry mouth (6)(7). In a study, it was found that the prevalence of xerostomia was 10.0% (with no apparent gender difference) among 32-year-olds and was significantly higher among those taking antidepressants (odds ratio =4.7) (5). At risk groups may present much higher (60+%) rates of xerostomia. A systemic literature review suggests a prevalence of 27 –32% of the medicated population suffer from xerostomia as a side effect (7).

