- The study team may terminate subjects if they no longer fulfill inclusion criteria, if an exclusion criterion is met, or if they do not show up for scheduled study visits.
- Subjects who experience an unanticipated adverse drug effect will be withdrawn from the study.
- Subjects unable to complete the study procedures due to a medical condition such as dry mouth and sensitivity conditions that result in the inability to capture meaningful data during the study procedures.
- Subjects may choose to withdraw from the study at any time.

Subjects may remain patients of TUSDM if they decide to withdraw from the study or are withdrawn by the study team.

If during the course of their participation in the study, a subject chooses to withdraw or is withdrawn by the research team, any data that has been

collected will not be included in the analysis and the subject will be asked to return any leftover whitening gel and the diary. The subject is able to keep the toothpaste and toothbrush.

Subjects will not be able to partially withdrawal from study intervention and just be involved with continued data collection.

The Principal Investigator will determine whether subjects (either withdrawn subjects or subjects completing the study) are in need of additional treatment and/or follow-up observation as a result of participation in this trial and will refer them to their primary care provider for further care. Subjects and/or their insurance will be responsible for the cost of any standard of care follow-up visits or additional treatment that is not part of this study.

4) Vulnerable Populations

Transgender subjects will be recruited as part of this study. All subjects will be asked on the Medical/Dental History Form to identify their sex, to which they will answer however they choose. They will not be sought out or targeted for participation and will not be discriminated against as a result of their sexual orientation/gender identity. The subjects will not be asked to disclose if they are transgender or not on the Medical/Dental History Form.

Cognitively impaired adults and pregnant adults will not be enrolled in this study. There would be no direct benefits to these specific vulnerable populations by enrolling them. Pregnancy will be determined through self-reporting.

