- 11. Photographs of subject teeth will be taken by a standard dental camera. The photos will only contain subject teeth and oral cavity with no subject identifiers visible. In addition to the ICF, the subjects will be asked to sign a photo release form. If the subject does not wish to sign this form, their photographs will not be taken. Those who do not consent to having their photos taken will be tracked in the enrollment log. Photographs will be taken pre-application of the study product at visit 1.
- 12. Distribution of study product and diary: One box of study whitening gel product, (0.88Oz) toothpaste, and a toothbrush will be dispensed by study team members. This is to ensure all participants are using the exact same dental products during the trial period. The subjects will be asked to not use any other oral tools or products during the trial period aside from the ones distributed by the study team at Visit 1. A diary will also be dispensed for the record keeping of the application of the products. A study team member will again verbally tell the participant the instructions that are provided with the study product and that per the

instructions, they can apply the product up to 4 times per day until their next study visit. The same script from step 9.a. will be used.

13. Gift card will be distributed upon successful completion of visit.

Visit 2 (1-1.5 hours) Final Visit - 7 ∓ 2 days after visit 1

- 1. Subject will be called 1-2 days before their appointment to confirm that in order to participate, they must:
 - a. Not consume alcohol for 24 hours prior to their visit.
 - b. Not brush their teeth for 1.5 hours prior to their visit.
 - c. Not have had anything to eat or drink (including chewing gum or eating candy) for 1.5 hours prior to their visit). Water is acceptable to drink up to 1 hour prior to the study visit.
 - d. Not smoke 1.5 hours prior to their visit.
- 2. Medical history will be reviewed, and any changes will be noted. Any changes to medications will also be reviewed and noted.
- 3. Eligibility and subject withdrawal criteria will be reviewed to ensure the subject still qualifies for the study.
- 4. Subject medications with potential side effects being dry mouth will be verified using the Physician's Reference Desk. Subjects will be asked to confirm that they have taken their medications as prescribed since Visit 1.

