- An oral exam, including evaluation of oral cavity, soft and hard tissues, will be completed following standard of care procedures in US dentistry using a mouth mirror and dental explorer.
- 6. Saliva Collection 1 (pre-product application): Saliva will be collected using the drooling method for 5 minutes into a pre-weighed vial. The post collection weight will be subtracted from the pre-weight to determine the flow rate. The saliva samples will be discarded after they are weighed.
- 7. The paper questionnaire will be given to subject to complete before application of study product and after application of study product. The questionnaire

- includes the Visual Analogue Scale (VAS) questionnaire on dry mouth, quantity of saliva, and perceived sensitivity of teeth.
- 8. Application of study product: A study team member will ask the subjects to apply the gel to their teeth. Subjects will then be asked to sit for 5 minutes to allow the gel to set on their teeth.
- 9. Saliva Collection 2 (post-product application): Saliva will be collected using the same drooling method as Saliva Collection 1. The saliva samples will be discarded after they are weighed.
- 10. Photographs of subject teeth will be taken by a standard dental camera. The photos will only contain subject teeth and oral cavity with no subject identifiers visible. Photographs will be taken post-application of the study product at visit 2.
- 11. The study diary and any leftover whitening gel product will be collected.
- 12. Gift card will be distributed upon successful completion of visit.

	Screening/ Baseline Visit Day 0	Visit 2 Day 7 (±2 days)
Informed Consent Form	X	Day 7 (±2 days)
Demographics	X	
Collect and/or Review Medical History	X	Х
Review eligibility and withdrawal criteria		Х
Confirmation of Xerogenic Medications	Х	
Pre-Product Use Dry Mouth & Sensitivity	Х	Х
Questionnaire		
Post-Product Use Dry Mouth & Sensitivity	x	Х
Questionnaire		
Unstimulated Salivary Test	x	Х
Oral Exam	x	Х
Evaluate eligibility criteria	x	
Oral Photographs	X (Pre-Application)	X (Post-Application)
Demonstration of Product Use	х	
Product Usage	X	X

Post Product Use Unstimulated Salivary Test	х	х
Product Distribution or Collection	X	X
Adverse Event Reporting (if applicable)	Х	Х
Stipend	Х	Х

G) Subject Safety

1) Adverse Event Reporting

Adverse Events

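### Xerogenic medication need not be stable at entry, and its timing is not matched between visits, so the Visit 1 to Visit 2 comparison can absorb drug-driven change

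*Combined protocol and SAP*

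**What the plan says.** All references are to the Combined protocol and SAP.

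- **Entry (III.D.1).** The medication criterion is "Evidence of currently taking Xerostomia-inducing medication such as, antihypertensives, anti-anxiety agents, psychiatric remedies, antihistamines". It sets no minimum duration, stable dose or pattern of use. Entry also needs a score of at least 5 on the question about dryness at that moment, and unstimulated flow no higher than 0.18 mL/min.
- **Background (II).** The drug effect is described as reversible: "Neural transmission is when the neuro transmission is hindered reversibly leading to the salivary hypofunction that results in dry mouth".
- **Pre-visit call (III.F, step 1 of both visits).** It covers alcohol, brushing, food, drink and smoking. It does not mention time since the last xerogenic dose or the clock time of the visit.
- **Visit 2 (III.F, steps 2 to 4).** "Any changes to medications will also be reviewed and noted"; "Eligibility and subject withdrawal criteria will be reviewed to ensure the subject still qualifies for the study"; xerogenic drugs are verified again; and "Subjects will be asked to confirm that they have taken their medications as prescribed since Visit 1".
- **Withdrawal (III.D.3).** "The study team may terminate subjects if they no longer fulfill inclusion criteria", and also if an exclusion criterion is met. For a withdrawn subject, any data "collected will not be included in the analysis".
- **Analysis (III.B).** t tests compare measurements before and after application, and the same method compares the first and final visits. Nothing addresses changed medication. The study is single-arm and open-label.
- **Schedule table (end of III.F).** The row "Confirmation of Xerogenic Medications" is marked at baseline only.

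**The concern.** III.A frames the study as the effect after one week's use. The Visit 1 to Visit 2 contrast in dryness and flow is the one that speaks to that, and no concurrent arm carries the background change. The enrolled population is defined by use of drugs that can dry the mouth reversibly. The protocol standardises food, smoking, toothpaste and toothbrush, but not the exposure that defines the population.

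A dose change, a switch, an added drug, an as-needed drug taken before one visit and not the other, or a different interval since the last dose could each move dryness and flow. In the between-visit comparison that movement cannot be told apart from the gel. Such differences can go either way, so they may bias the result, mask an effect or add noise.

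**Working it through.** **1. Which drug differences the existing rules reach**

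| Difference at Visit 2 | What the plan does |
|---|---|
| All xerogenic drugs stopped | Inclusion no longer met; termination is discretionary and, if used, the data are dropped |
| Drug change that lifts flow above 0.18 mL/min | By its wording an exclusion criterion is met; termination is discretionary, and the review (step 3) comes before the saliva collection (step 6) |
| Prescribed dose change, switch or added drug, still qualifying | Noted; consistent with use as prescribed; no analysis rule |
| As-needed drug taken before one visit only | Can be consistent with use as prescribed; no rule |
| Different time since last dose or time of day | Not recorded, not matched |

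The last three rows are the gap.

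**2. The plan's own figure**

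The 25 subjects in III.B cannot be reproduced, because no effect size, SD, alpha, sidedness or power is given. A paired t test with n = 25 and two-sided alpha 0.05 corresponds to a standardised mean change of 0.584 at 80% power and 0.676 at 90%. This gives a scale only; it neither supports nor weakens the point.

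**3. Illustration: some subjects change drug exposure**

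Assumed: no gel effect, n = 25, and k subjects each shifted by s SDs of the change score. Mean shift = k × s / 25. The probability of a significant improvement is simulated with a paired t test (nominal 2.5% in that direction).

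- k = 1, s = 1: 1/25 = 0.04 SD; 3.6%
- k = 2, s = 1: 2/25 = 0.08 SD; 5.1%
- k = 3, s = 2: 6/25 = 0.24 SD; 11.6%
- k = 5, s = 2: 10/25 = 0.40 SD; 27.5%

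Shifts towards worse dryness give the same sizes with the opposite sign and would hide a benefit. If two subjects improve by 1 SD and two worsen by 1 SD, the mean shift is (2 − 2)/25 = 0. The expected sample variance then rises from 1 to 1 + 4/24 = 1.17, which is noise and not bias.

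**4. Illustration: unmatched timing plus the entry threshold**

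Assumed: dryness at a visit = subject level (mean μ, SD 2) + residual (SD 1) + dose-timing component (SD τ), all normal; entry at a score of 5 or more at Visit 1; no gel effect. Let σ = √(4 + 1 + τ²), a = (5 − μ)/σ and λ = φ(a)/(1 − Φ(a)). The expected spurious drop is:

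- timing unmatched: (1 + τ²) × λ / σ
- timing matched (same component at both visits): 1 × λ / σ

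For μ = 5 and τ = 1: σ = √6 = 2.449 and λ = 0.798, so the drop is 2 × 0.798/2.449 = 0.65 unmatched and 0.798/2.449 = 0.33 matched.

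| μ | τ | Drop, unmatched | Drop, matched | P(significant improvement), unmatched / matched |
|---|---|---|---|---|
| 5 | 0 | 0.36 | 0.36 | about 24% either way |
| 5 | 0.5 | 0.44 | 0.35 | 28% / 23% |
| 5 | 1 | 0.65 | 0.33 | 38% / 21% |
| 6 | 0 | 0.24 | 0.24 | 13% / 13% |
| 6 | 1 | 0.45 | 0.23 | 21% / 12% |

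The τ = 0 rows show that much of the drop is ordinary regression to the mean, which matching does not remove. The part due to unmatched timing is the difference between the drop columns: at μ = 5, about 0.09 points for τ = 0.5 and 0.32 for τ = 1. The flow threshold selects in the same way but is not modelled here.

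**The case against.** The strongest reply is that the plan is not silent on medication between visits. It notes changes, re-verifies the drugs, asks about use as prescribed, re-reviews eligibility and permits termination with the data dropped. The window is only 7 ± 2 days, so few prescriptions will change. The study is exploratory, and its largest limitation, the missing control, stays whatever is done about medication.

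Much of that stands. The Visit 2 steps are a real partial safeguard, and the short window limits prescription changes. It does not limit differences in dose timing, which can affect any subject. The safeguards also stop short of the subject who changes and still qualifies.

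Several stronger readings are tempting, and the documents do not support them:

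- *Any drug change will pass as a gel effect throughout the study.* The pre/post-application comparison sits inside one visit of 1 to 1.5 hours around a 5-minute set, so a change between visits largely cannot produce it.
- *Entry favours people just dosed or early in a course, so later changes lean towards improvement.* The documents give no pharmacokinetic, onset or tolerance data. A direction arises mainly through selection on the momentary score and flow.
- *A repeat baseline would not help.* For the timing part it would partly help, since that part works through selection on a single reading. It would not remove a true change of drug.
- *Every subject's dryness is caused by a drug.* The criteria require current use and exclude some other causes; they do not establish causation.

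The schedule-table mismatch is weak evidence by itself. The table is visibly disordered in the text as read from PDF, so a mark may have been lost, and step 4 is explicit.

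**Conclusion.** The point holds for the Visit 1 to Visit 2 comparison of dryness and flow, and only there. Nothing requires stable xerogenic medication at entry, nothing matches or records dose timing, and no analysis rule covers a subject whose exposure differs but who still qualifies. With no control arm, those differences are confounded with one week of gel use.

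Drug changes alone have no known direction. Unmatched timing does lean towards apparent improvement, because entry selects on a high momentary score and a low flow at the same visit.

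The size cannot be established from the documents. In the illustrations it runs from almost nothing (0.04 SD, or zero with added noise) to 0.40 SD for drug changes, and from about 0.09 to 0.32 points for unmatched timing at an assumed population mean of 5. These figures rest wholly on the assumed number, size and direction of changes and on the assumed variance components. They show the mechanism and do not predict this trial's bias. The change is worth making because it is cheap, not because the bias is shown to be large.

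**What to change.** 1. **III.D.1:** add that xerogenic medication has been stable (same drugs, dose and pattern of use) for a sponsor-defined period before Visit 1, with no change planned through Visit 2. This is an eligibility condition only; no subject's prescribed treatment is altered.
2. **III.F:** book both visits at a similar time of day, and record at each visit the time of the last dose of each xerogenic drug.
3. **III.B:** for subjects with a noted medication change who are not terminated under III.D.3, keep them in the main analysis, flag them, and repeat the between-visit dryness and flow comparisons without them.
4. **Schedule table:** reconcile the medication-confirmation row with Visit 2 step 4, after checking the table in the source file.

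The cost is one eligibility sentence, one booking instruction, one case report form field per visit and one additional analysis. There would be a few more screen failures, in a plan that already provides for 100 screened against 25 needed, and less flexible booking. This reduces the problem but does not replace a concurrent control.
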